Using the following equation to calculate sample size for proportional outcomes in randomized controlled trials and using data from a 2012 study by Paul et. al. citing a 58% overall compliance with PALS severe sepsis target times:

$$m \text{ (size per group)} = c \times \frac{\pi_1(1 - \pi_1) + \pi_2(1 - \pi_2)}{(\pi_1 - \pi_2)^2}$$

where c is set at 7.9 for a power of 80%

π_1 is current percent success rate on standard protocol

π_2 is the current percent success plus the anticipated treatment effect percent

We have calculated the total number of subjects in the sepsis arm to be: 82 per group or 164 total patients for a power of 80% and a type I error set at 5%

For the gastroenteritis and dehydration arm we have established a sample size using the following power calculation for continuous (time) outcomes

	Protocol Name:	Randomized Controlled Trial of Inferior Vena Cava Ultrasonography in the Management and Disposition of Pediatric Patients Undergoing Evaluation for Sepsis and Dehydration
	Principal Investigator:	[name] [contact] [contact] or [contact]
	Primary Contact Name/Contact Info:	[name] [contact]
	Date Revised:	2/10/2015
	Study Number:	IF1733382

$$\text{Total sample size} = \frac{c}{\delta^2} + 2$$

where c is set at 7.9 for a power of 80%

δ^2 is set for a 10% size treatment effect (reduction in time)

We would need 200 subjects per group or a total of 400 patients in the gastroenteritis arm of the study.

d) Study Timelines

Currently the Mount Sinai Pediatric Emergency Department sees approximately 30,500 patients on an annual basis. Of this total census about 200 trigger the Stop Sepsis alert upon registration. Based on this we have set the enrollment period over 12 months.

Current census data predicts approximately 3000 Mount Sinai annual emergency department visits for vomiting and dehydration requiring antiemetic therapy. In order to collect a convenience sample of 400 patients and adjust for seasonal variability, the study period will enroll over a six month period between June 2015 and November 2015.

e) Study Endpoints

For the Sepsis arm endpoints include:

Primary

- Secured second vascular access point- type (IO, second IV, CV access) within 15 min of physician evaluation
- Inotrope/Vasopressor use
- Antibiotic within 60 min

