	Protocol Name:	Randomized Controlled Trial of Inferior Vena Cava Ultrasonography in the Management and Disposition of Pediatric Patients Undergoing Evaluation for Sepsis and Dehydration
	Principal Investigator:	[name] [contact] [contact] or [contact]
	Primary Contact Name/Contact Info:	[name] [contact]
	Date Revised:	2/10/2015
	Study Number:	IF1733382

- 60 ml/kg Normal Saline bolus administered within 60 minutes

Secondary

- Disposition- PICU, Floor, Discharge
- Length of ED stay (from sepsis alert to admission/discharge order entry)
- Return ED Visit for same illness
- Survival to hospital discharge
- 30 day mortality
- Left ventricular function
- Source of sepsis

For the Gastroenteritis/Dehydration arm endpoints include:

Primary

- Type of rehydration: oral versus intravenous
- Total amount of fluids given (ml amount)
- Total ED length of stay from triage time to disposition time (order to admit/discharge)

f) Procedures Involved in the Human Research

Allocation of patients to intervention and control arms will be accomplished by a computer generated randomization application Sherlock MD®. Randomization will be separate for sepsis cohort and gastroenteritis cohort. Within sepsis and gastroenteritis cohorts, subjects will be stratified by disease severity. Specifically they will meet criteria for severe sepsis or meet criteria for severe dehydration based on standard clinical severity scoring (e.g. SIRS criteria, Clinical Dehydration Score).

Subjects randomized to either arm will receive diagnostic imaging of the inferior vena cava with ultrasound. Subjects randomized to the investigational arm will undergo IVC ultrasound immediately

	Protocol Name:	Randomized Controlled Trial of Inferior Vena Cava Ultrasonography in the Management and Disposition of Pediatric Patients Undergoing Evaluation for Sepsis and Dehydration
	Principal Investigator:	[name] [contact] [contact] or [contact]
	Primary Contact Name/Contact Info:	[name] [contact]
	Date Revised:	2/10/2015
	Study Number:	IF1733382

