	Protocol Name:	Randomized Controlled Trial of Inferior Vena Cava Ultrasonography in the Management and Disposition of Pediatric Patients Undergoing Evaluation for Sepsis and Dehydration
	Principal Investigator:	[name] [contact] [contact] or [contact]
	Primary Contact Name/Contact Info:	[name] [contact]
	Date Revised:	2/10/2015
	Study Number:	IF1733382

The ultrasound images and clips are not saved in the permanent medical record in EPIC. However, all images are saved in an ultrasound archive supported and secured by Mount Sinai Medical Center IT Department and is HIPAA compliant.

i) Provisions to Monitor the Data to Ensure the Safety of subjects

In order to ensure that adequate provisions are in place for monitoring the data to ensure the safety of subjects, ultrasound image review for quality assurance (QA) will occur weekly during the study. Images will be reviewed to determine the presence or absence of total inferior vena collapse and presumed severe dehydration (as well as other pathology). If the 2nd (QA) interpretation is positive for pathology. The EPIC record will be reviewed to see if the patient was treated with appropriately given the QA read findings. If there are any discrepancies or pathological findings noted on the image review, there is a procedure in place to contact patients and institute any changes in treatment, if necessary. Previous studies site good interobserver agreement with a Cohen's Kappa = 0.64. In accordance we anticipate that a discrepancy between ultrasound interpretations will happen rarely.

A DSMB will be formed from personnel not participating in this trial. This board will include a senior scientist and an ethicist. To monitor for safety problems, adverse events will be reported to the DSMB. An interim data analysis is planned when study enrollment reaches (25% enrollment) 40 patient in the sepsis arm and 100 in the gastroenteritis arm to ensure no excess rates of adverse events are observed in the intervention group compared with the control group.

The primary responsibility of the DSMB is to ensure the safety of the patients. None of the members will be investigators in the study.

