## Gastroenteritis Statistical Plan

We calculated the sample size required to provide more than 80% power (with a two-sided alpha level of 0.05) to detect an absolute difference of 15% in PO vs. IV rehydration or more between groups. We estimated a sample size of 200 patients for the gastroenteritis section of the study.

Enrolled Patients are to be randomized to immediate versus delayed US assessment of the IVC in patients aged 0-21 years who presented to an emergency department with vomiting requiring ondansetron or with diarrhea possibly requiring IV rehydration. Patients enrolled were randomized to assessment of dehydration by clinical exam plus US (immediate) or clinical exam alone and then US 15 minutes later (delayed). Clinical dehydration scores were recorded prior to IVC US. Decision to treat with IV versus PO rehydration, pre-test and post-test probabilities were recorded before and after US. Primary outcomes included IV versus PO rehydration based on intent-to treat principle; secondary outcomes included median total ED length of stay (EDLOS; triage time to disposition) time failure of PO rehydration, and disposition (ED discharge vs admission). All outcomes between groups were compared by using a Pearson chi-squared test. The alpha level was set at .05 for all analyses, 95% CIs were calculated, and all comparisons were two tailed. Data analysis was performed with the use of SPSS 20.0 (IBM).

We calculated the sample size required to provide more than 80% power (with a two-sided alpha level of 0.05) to detect an absolute difference of 15% more more between arms in the number of patients receiving antibiotics with 60 minutes between groups. We estimated a sample size of 200 patients for the sepsis section of the study.

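### The gastroenteritis sample size of 200 per group (400 total) does not follow from the protocol's own formula, and its 80% power claim has no stated SD behind it

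*Protocol*

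**What the plan says.** Protocol section 5c bases the gastroenteritis calculation on a continuous time outcome. It prints a formula for the total sample size, c/δ² + 2, sets c = 7.9 for 80% power, and says that δ² "is set for a 10% size treatment effect (reduction in time". The conclusion is "We would need 200 subjects per group or a total of 400 patients in the gastroenteritis arm of the study".

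The time outcome is evidently the one listed among the three gastroenteritis primary endpoints in section 5e: "Total ED length of stay from triage time to disposition time (order to admit/discharge".

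The number is used again. Section 5d plans the enrolment window "In order to collect a convenience sample of 400 patients and adjust for seasonal variability", and section 5i places the interim safety look at "25% enrollment) 40 patient in the sepsis arm and 100 in the gastroenteritis arm".

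The SAP (Gastroenteritis Statistical Plan) sizes the same cohort differently. It claims power above 80% "to detect an absolute difference of 15% in PO vs. IV rehydration or more between groups", and says: "We estimated a sample size of 200 patients for the gastroenteritis section of the study". It moves the time outcome down a level ("secondary outcomes included median total ED length of stay") and applies Pearson's chi-squared test to every outcome.

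**The concern.** Section 5c prints its formula, its constant and its effect size, so a reader should be able to reach 200 per group or 400 in total. Neither reading of the 10% effect gives either figure. Two further problems lie behind the arithmetic:

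- The expression c/δ², with δ as a difference in SD units, has the form used for one sample or for paired data. This trial compares two independently randomised groups.
- A 10% reduction is a relative change. It becomes a δ only once the SD is known relative to the mean, and no mean or SD for any time outcome appears in the text provided.

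This is the only calculation behind the protocol's 400. If it cannot be reproduced, nobody can say what difference the trial could detect, or what a null result on length of stay would mean. The SAP offers a different total for the same cohort, and its power claim also depends on an omitted figure, the baseline proportion.

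**Working it through.** **Inputs.** From Protocol 5c: c = 7.9 (80% power; this value corresponds to two-sided 5%), a 10% effect, total N = c/δ² + 2, and a stated result of 200 per group or 400 total. From the SAP: 200 patients and a 15-point difference. Assumed, because not stated: SD/mean of length of stay, the baseline IV or PO proportion, and equal allocation under the SAP (100 per group).

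**1. The printed formula.**

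- δ² = 0.10 (literal wording): 7.9/0.10 + 2 = 81 total.
- δ = 0.10: 7.9/0.01 + 2 = 792 total.
- Back-solving for a total of 400: δ = √(7.9/398) = 0.141.
- Back-solving for 200: δ ≈ 0.20, since 7.9/0.04 + 2 = 199.5. The formula labels this a total, whereas the text uses 200 per group.

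Neither 0.141 nor 0.20 appears in the documents. A δ of 0.20 would arise from a 10% reduction with SD/mean of 0.50 (0.10/0.50), but that is a guess at the origin.

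**2. The two-group form.** With δ in SD units, n per group = 2c/δ².

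- δ² = 0.10: 15.8/0.10 = 158 per group.
- δ = 0.20: 15.8/0.04 = 395 per group.
- δ = 0.10: 15.8/0.01 = 1580 per group.

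Power of a two-sample t-test with 200 per group is 88% at δ = 0.316 (δ² = 0.10), 51% at 0.20 and 29% at 0.141. The last two are the effects at which the printed formula returns 200 and 400; they are not estimates of the trial's power.

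**3. What the missing SD does.** For a 10% lower mean, δ = 0.10/(SD/mean).

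| Assumed SD/mean | δ | Power, 200 per group | Power, 100 per group |
|---|---|---|---|
| 0.25 | 0.40 | 98% | 80% |
| 0.30 | 0.33 | 91% | 65% |
| 0.36 | 0.28 | 79% | 50% |
| 0.50 | 0.20 | 51% | 29% |
| 1.0 | 0.10 | 17% | 11% |

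At 200 per group, 80% power needs δ of about √(15.8/200) = 0.281, so SD/mean of at most 0.10/0.281 = 0.36. For a rank-based test of a 10% lower median, assuming log-normal times (relative efficiency 0.955), the detectable δ is 0.281/√0.955 ≈ 0.287 on the log scale. The log-SD must then be at most −ln(0.90)/0.287 ≈ 0.37.

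**4. Whether the SAP's figure stands in its place.** Using the proportions formula printed in 5c for the sepsis cohort, n per group = 7.9 × [p₁(1−p₁) + p₂(1−p₂)]/0.15²:

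| Proportions | n per group needed | Chi-squared power, 100 per group | Chi-squared power, 200 per group |
|---|---|---|---|
| 10% vs 25% | 7.9 × 0.2775/0.0225 = 97.4 | 80% | 98% |
| 20% vs 35% | 7.9 × 0.3875/0.0225 = 136.1 | 66% | 92% |
| 50% vs 65% | 7.9 × 0.4775/0.0225 = 167.7 | 57% | 86% |
| 42.5% vs 57.5% (largest n) | 7.9 × 0.48875/0.0225 = 171.6 | 57% | 85% |

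At 100 per group the SAP's claim holds only if the lower proportion is about 10% or less, or by symmetry the higher is about 90% or more.

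**5. The interim look.** 100/400 = 25%, which matches 5i. 100/200 = 50% under the SAP's total.

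**The case against.** The strongest reply concerns the scale of δ. If δ meant the difference divided by twice the SD, c/δ² would already be the correct two-group total. A total of 400 would then correspond to 2 × 0.141 = 0.282 SD, at which 200 per group does have about 80% power. Nothing in 5c supports that scale, since δ² is tied to a 10% effect. On that scale the formula still returns 792 or 81, not 400. What stands is that δ is undefined, and that the 51% and 29% figures depend on reading it in ordinary SD units.

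Second, if δ² = 0.10 is taken literally in SD units, 200 per group is more than enough (88%). That is so, but 0.316 SD equals a 10% reduction only when SD/mean is 0.10/0.316 = 0.316, which is again unstated.

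Third, the SAP makes IV versus PO primary and length of stay secondary, so the disputed calculation may no longer size anything. That would be a reason to delete it, but the protocol still rests its 400 on it. The SAP's own total differs by a factor of two and lacks its key input.

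Fourth, the look at 100 patients is a safety look with no efficacy boundary described, so the 25% versus 50% mismatch has no shown effect on type I error. That is fair: it is a matter of consistency only.

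**Conclusion.** The concern holds. The protocol's 200 per group and 400 total cannot be obtained from its formula at a 10% effect, and the accompanying 80% power is unsupported. The trial is not shown to be underpowered: 400 would suffice for a 10% shorter mean stay if SD/mean were about 0.36 or less, and would give 51% power at 0.50. These figures assume two equal independent groups, two-sided 5% and a t-test on the mean.

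The visible SAP does not rescue the number. On its 200 patients, assumed to be split equally, power for 15 points runs from 80% at 10% versus 25% down to about 57% near the middle of the range. Whichever document governs, its power claim rests on a figure that is not given, and the two totals conflict. This needs correcting before either document can be relied on.

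**What to change.** 1. **Protocol 5c.** Name the time outcome, use n per group = 2c/δ² with δ in SD units, and state the assumed SD and its source. If IV versus PO is to be the sole primary outcome, delete this calculation.
2. **Detectable effect at 80% power.** For length of stay, state about 0.28 SD at 200 per group or 0.40 SD at 100 per group (about 0.29 and 0.41 on the log scale for a rank-based test). For IV versus PO, state the baseline proportion. Near 50%, the detectable difference is about 14 points at 200 per group or 19 to 20 points at 100 per group.
3. **SAP test for length of stay.** Replace chi-squared with a method for a continuous, skewed time. A rank-based or median comparison fits the planned median; a comparison of log-means is an alternative.
4. **One primary outcome and one total in both documents.** Make the 400 in 5d and the percentage and count in 5i agree with it. If the SAP's 200 is kept, restate its power or detectable difference as in item 2.

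The cost is wording in Protocol 5c, 5d, 5i and the SAP, plus a detectable effect that may look better or worse once the SD and baseline are stated. No added enrolment is required. It rises only by choice. Adopting the protocol's 400 adds 200 patients to the SAP's number and gives at least 85% power for 15 points at any baseline. Holding a 10% target at 80% power with SD/mean of 0.50 would need 395 per group.

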Ultrasound is a widely accepted and highly useful clinical tool. It carries the additional advantage of being rapid, painless and non-radiating. It has long been used to assess cardiac output and vascular pathologies. More recently emergency and trauma clinicians have been using it to assess hydration status, shock/sepsis states and fluid responsiveness (nguyen). Using sonography to look at the inferior vena cava gives clinician a rapid view of vascular collapsibility that has been previously demonstrated to correlate with MAP and CVP (Sinonson/schiller, Stone/Huang). Previously Jones et. al. completed an RCT in adults greater than age 17 evaluating the goal directed utility of early versus delayed inferior vena cava sonography for patients presenting with non traumatic hypotension to the emergency department. This study found improved outcomes and more accuracy in diagnostic etiology of in those undergoing immediate IVC imaging.

	Protocol Name:	Randomized Controlled Trial of Inferior Vena Cava Ultrasonography in the Management and Disposition of Pediatric Patients Undergoing Evaluation for Sepsis and Dehydration
	Principal Investigator:	[name] [contact] [contact] or [contact]
	Primary Contact Name/Contact Info:	[name] [contact]
	Date Revised:	2/10/2015
	Study Number:	IF1733382

3) Setting of the Human Research- The Emergency Department of Mount Sinai Hospital

4) Resources Available to Conduct the Human Research –

Internal resources from the Department of Emergency Medicine.

5) Study Design – A randomized controlled trial of IVC Ultrasonography in pediatric patients 0-21 year of age.

a) Recruitment Methods

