upon arrival and clinician evaluation. Those subjects randomized to the control arm will undergo IVC ultrasound after a timed 15 minute delay. The IVC will be scanned in both longitudinal and transverse planes. All study clinicians will undergo brief 20 minute standardized training session to review which images to obtain.. Still and dynamic images will be recorded and saved. Imaging procedure involves a credentialed ultrasound clinician using an ultrasound machine to visualize the inferior vena cava in order to assess the collapsibility and respiratory variation. This vessel is visualized by placing the ultrasound probe on the subxiphoid area of the abdomen using transducer gel. Images will be obtained in two axes (transverse and sagittal). Images/video will be recorded and stored using a unique study subject number to assure that health information remains confidential and de-identified. Treatment and management decisions will be at the discretion of the treating clinician. The enrolling clinician will be responsible for obtaining consent, randomization and completing the data collection forms. As indicated by the study inclusion criteria, all participants who have triggered the electronic Severe Stop Sepsis notification or have clinically suspected dehydration due gastroenteritis or vomiting will be screened and consented by the enrolling clinician. Given the published data that suggests inferior vena cava ultrasound may help clinicians more effectively and efficiently treat sepsis and dehydration, the main objective of this study is to see if it can reliably improve outcomes as well as improve compliance with targeted treatment goals. We believe that clinical care of subjects who undergo Inferior vena cava US is unlikely to be altered in a negative way.

g) Specimen Banking

Not applicable

h) Data Management and Confidentiality

During the process of data collection, patient identifiers will be collected (first and last name, MR#, age, birth date, date of visit. This identifying information is necessary for US will be located on only 1 form. This form will be kept in a locked file cabinet in a locked office remaining on the medical campus of Mount Sinai Hospital at all times.

Data forms will be kept in a secure locked file. HIPAA-sensitive Personal Health Information (PHI) will not be reused or disclosed to any other person or entity, except as required by regulation and law or for authorized oversight of the research project.

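### Fluid volume in raw mL is a protocol primary endpoint for ages 0 to 21 with no account taken of body weight, which can cost substantial power; adjust for baseline weight if the endpoint is kept

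*Protocol*

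**What the plan says.** Protocol section 5 e) (Study Endpoints) gives three primary endpoints for the gastroenteritis/dehydration arm: the route of rehydration, "Total amount of fluids given (ml amount", and ED length of stay. Section 5 describes "A randomized controlled trial of IVC Ultrasonography in pediatric patients 0-21 year of age", and the SAP's Gastroenteritis Statistical Plan keeps the same range: "immediate versus delayed US assessment of the IVC in patients aged 0-21 years who presented to an emergency department with vomiting requiring ondansetron".

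For the sepsis arm, the same section 5 e) states the fluid endpoint per kilogram: "60 ml/kg Normal Saline bolus administered within 60 minutes".

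On randomisation, section 5 f) says: "Within sepsis and gastroenteritis cohorts, subjects will be stratified by disease severity". Age and weight are not strata. On fluid given, section 5 f) says: "Treatment and management decisions will be at the discretion of the treating clinician". It states no volume rule for the gastroenteritis arm.

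The available SAP text makes IV versus PO rehydration the gastroenteritis primary outcome. Its secondaries are ED length of stay, failure of PO rehydration, and disposition. Fluid volume is in neither list. The only test named is Pearson's chi-squared, which neither suits a continuous volume nor adjusts for weight.

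**The concern.** Ultrasound may change how much fluid a child receives for their size, but it cannot change their size. In raw millilitres, an infant and a young adult given the same fluid per kilogram differ several-fold, and all of that spread enters the error term of an unadjusted comparison. The protocol already expresses fluid per kilogram in one cohort and not in the other.

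What is at stake is precision on an endpoint that the protocol calls primary. A real difference in fluid given could be missed because patients differ in size.

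**Working it through.** **The plan's own figure.** There is none for fluid volume: no SD, weight distribution or expected effect. Protocol section 5 c) sizes this arm at 200 per group on time ("δ^2 is set for a 10% size treatment effect (reduction in time"). The printed formula c/δ² + 2 with c = 7.9 and δ = 0.10 gives 7.9/0.01 + 2 = 792. It gives 199.5 at δ = 0.20. That mismatch is a separate matter and is not evidence here. I use 200 per group (protocol) and 100 per group (the SAP's 200 patients, if split equally) only as illustrative sizes.

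**Inputs.** All coefficients of variation (CVs) are my assumptions: weight CVw = 0.5 to 0.9, mL/kg CVf = 0.3 to 1.0.

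**Step 1: volume proportional to weight.** Let mL = weight × (mL/kg), the two factors independent. Then:

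- CV(mL)² = (1 + CVw²)(1 + CVf²) − 1
- patients needed with raw mL relative to mL/kg, same relative effect: CV(mL)² / CVf²
- share of the mL variance explained by weight: R² = CVw² / CV(mL)²
- patients needed with unadjusted mL relative to mL with a linear weight covariate: 1/(1 − R²)

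| CVw | CVf | CV(mL)² | raw mL vs mL/kg | R² of weight | unadjusted vs adjusted mL |
|---|---|---|---|---|---|
| 0.5 | 0.3 | 0.3625 | 4.03 | 0.69 | 3.2 |
| 0.5 | 0.5 | 0.5625 | 2.25 | 0.44 | 1.8 |
| 0.5 | 1.0 | 1.5000 | 1.50 | 0.17 | 1.2 |
| 0.7 | 0.3 | 0.6241 | 6.93 | 0.79 | 4.7 |
| 0.7 | 0.5 | 0.8625 | 3.45 | 0.57 | 2.3 |
| 0.7 | 1.0 | 1.9800 | 1.98 | 0.25 | 1.3 |
| 0.9 | 0.3 | 0.9729 | 10.81 | 0.83 | 6.0 |
| 0.9 | 0.5 | 1.2625 | 5.05 | 0.64 | 2.8 |
| 0.9 | 1.0 | 2.6200 | 2.62 | 0.31 | 1.4 |

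**Step 2: the middle case (CVw 0.7, CVf 0.5) as power.** At 200 per group, two-sided 0.05 and 80% power, the detectable standardised difference is 0.280. The residual CV of weight-adjusted mL is √(0.8625 − 0.49) = 0.610.

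- Raw mL: 0.280 × √0.8625 = 26% of the mean
- mL adjusted for weight: 0.280 × 0.610 = 17%
- mL/kg: 0.280 × 0.5 = 14%

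Power for a 20% reduction is 0.58 for raw mL, about 0.9 for adjusted mL (normal approximation: 0.20/0.610 × √(200/2) − 1.96 = 1.32) and 0.98 for mL/kg. At 100 per group the detectable standardised difference is 0.396, giving 37%, 24% and 20%.

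**Step 3: oral and IV patients mixed.** This was simulated with assumed age-weight curves (CVw 0.55 to 0.58). Half the patients took oral volumes spread over a tenfold range per kg. Half received one to three equal weight-based IV portions, with or without a cap on the portion. Raw mL then needs 1.5 to 1.9 times the patients of mL/kg, and weight explains 26% to 31% of the variance. By 1/(1 − R²), the covariate gain is about 1.35 to 1.45.

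**Step 4: volume not proportional to weight.** Simulated with volume proportional to weight^b and CVf 0.4 or 0.8, the ratio of patients (raw mL to mL/kg) is:

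- b = 1: 1.8 to 3.4
- b = 0.75: 1.4 to 2.0
- b = 0.5: 0.8 to 1.0
- b = 0.25 or 0: 0.15 to 0.74, so dividing by kg loses precision

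A linear weight covariate does not carry this risk. In a 1:1 randomised comparison of this size it costs essentially one degree of freedom if weight explains nothing.

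**Step 5: is it the same comparison?** In the simulation with mostly young patients, a 20% cut confined to those of 15 kg or less changed mean mL by −5.3% and mean mL/kg by −9.0%. Confined to those above 40 kg, the changes were −2.7% and −1.0%. The two scales agree only if the relative effect is constant across weights.

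**The case against.** The strongest reply is that the target is marginal. The available SAP text neither lists nor analyses fluid volume, and neither document's sample size rests on it, so no stated power claim changes. This stands as a reason to rank the point below the disagreement between the two endpoint lists. It does not remove the point, because the protocol still names the endpoint as primary. Part of the SAP was not available, so I cannot say that the whole SAP omits it.

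Four stronger readings are tempting, and the documents do not support them:

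- **That weight dominates the variance.** No CV is given. Weight's share runs from 17% to 83% over the assumed range, and an oral/IV mix pushes it down.
- **That mL/kg gives the same comparison more precisely.** Mean mL lets heavier patients count for more (Step 5), and the gain needs volume to be roughly proportional to weight. The only support for that is a sepsis endpoint from a separately randomised cohort; in gastroenteritis, fluid is left to the clinician.
- **That weight imbalance biases the result.** Randomisation balances weight in expectation, and chance imbalance is already in the standard error. With CVw 0.7 and 200 per group, the SE of the difference in mean weight is 0.7 × √(2/200) = 7% of the mean. That is the same noise seen another way, not a second harm.
- **That the change needs no new data.** The per-kilogram endpoint shows a need for weight in sepsis only. The data items listed under data management and monitoring do not include weight. Those lists mainly concern identifiers, so they do not show that weight is missing either.

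**Conclusion.** The point holds in a limited form. The protocol names raw millilitres as a primary endpoint across ages 0 to 21 and plans nothing to account for body size, so an unadjusted comparison can waste substantial power. It does not bias the comparison.

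The size rests wholly on assumed CVs. With volume proportional to weight, raw mL needs about 1.5 to 11 times the patients of mL/kg, or about 1.5 to 1.9 times with the assumed oral/IV mix. With scaling near weight^0.5 or flatter, dividing by kg brings no gain or a loss. Covariate adjustment for weight is the conclusion that survives all of these cases. Its gain is smaller (about 1.2 to 6 times under proportionality) but does not depend on proportionality being true.

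**What to change.** First decide whether fluid volume remains an endpoint: primary as in the protocol, or secondary once the protocol and SAP lists are reconciled. If it remains:

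- Compare arms with baseline ED weight as a covariate, in place of an unadjusted comparison of raw mL. Fix one of two forms in advance. The first is mL with a linear weight term and robust standard errors, which keeps the difference in mean mL as the quantity estimated. The second is log mL adjusted for log weight, which lets the data set the scaling but needs a rule for zero volumes.
- Report mL/kg by arm alongside. State that the mL/kg and log-scale results estimate a somewhat different effect from mean mL unless the relative effect is constant across weights.
- Confirm that ED weight is on the gastroenteritis data form, and add it if not.

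The cost is a line in the endpoint definition, a sentence in the SAP and possibly one data field. Randomisation, treatment and sample size do not change.
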